6 STUDY CONDUCT

The Investigator will agree to perform all aspects of this study in accordance with the ethical principles that have their origin in the Declaration of Helsinki, ICH E6(R2): GCP, the protocol, and all national, state, and local laws or regulations.

This Phase 2B study will consist of:

- A Screening period (Days -45 to -4)
- Pretreatment with ASA 81mg daily (Day -7 to Day 1)
- Check-in Day–admission to study clinic (Day -3 to Day 3)
- Pretreatment and ticagrelor treatment (Day -2 to Day 1)
- On-site Randomization/Treatment (Day 1)
- 2-Day on-site Follow-up period (Day 1 to Day 3)
- Day 7 Follow-up visit (Day 7)
- Final Follow-up visit on (Day 35+3)

Plasma samples for PD and PK analysis of PB2452, ticagrelor and its active metabolite, (TAM) will be collected at Day -2, pre-dose (within 10 minutes prior to start of infusion), Day 1 and Day 2 at 5, 10 and 30 minutes and 1, 2, 4, 8, 12, 20, 24, 36, 48 hours following initiation of the study drug infusion. Plasma PK samples will also be collected on Day 7, and Day 35±3 after initiation of study drug infusion.

Safety and tolerability will be carefully monitored through the study. The existence of anti-drugantibodies will be assessed in all subjects at Day -3, Day 1 (randomization), Day 7 and 35 ± 3 following administration of study drug at 3 months and then every 6 months until return to baseline.

The estimated duration of the study for each subject, excluding screening, is approximately 35 ± 3 days.

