6.2 Discontinuation or Withdrawal

6.2.1 Individual Subjects

6.2.1.1 Treatment Discontinuation

A subject may withdraw consent and discontinue from the study at any time, for any reason, without prejudice to further treatment. Subject participation in the study may be stopped at any time at the discretion of the Investigator or at the request of the Sponsor, or if the study is terminated.

The Investigator may withdraw a subject from the study if the subject:

- Is non-compliant with the protocol
- Experiences a serious adverse event (SAE) or intolerable adverse event (AE) that, in the Investigator's opinion, requires withdrawal from the study
- Has laboratory safety assessments that reveal CS hematological or biochemical changes from baseline values
- During the course of the study and through the end of study develops symptoms or conditions listed in the exclusion criteria
- Requires a medication prohibited by the protocol
- Requests an early discontinuation for any reason

If a subject experiences a SAE or an intolerable adverse event (AE) that requires discontinuation in the opinion of the Investigator or as reported by the subject, then the Investigator may confer with the Sponsor regarding disposition of the subject. If a subject is discontinued from treatment because of an AE, the event will be followed until it is resolved or until the AE is stable in the opinion of the Investigator.

When a subject withdraws or is withdrawn from the study, the reason(s) for withdrawal will be recorded by the Investigator on the relevant page of the electronic case report form (eCRF). Whenever possible, any subject who withdraws from the study if willing, should continue to be followed according to the protocol. For example, if termination occurs earlier than planned (i.e., after a subject has received all or partial study drug infusion) all efforts should be made to ensure the remaining protocol visits are completed. If a subject refuses to return for the Follow-up visits, the Day 35 ± 3 visit procedures should be completed to the extent possible, and the site should try contacting the subject at least 3 times by letter, certified letter, phone call, email or other reasonable methods. All attempts to contact subjects and the final status of subjects who fail to complete final assessments will be documented in the source documents.

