6.2.1.2 Withdrawal from Study

Subjects may withdraw from the study at any time at their own request or they may be withdrawn at any time at the discretion of the Investigator or Sponsor for safety, behavioral, or administrative reasons. If a subject does not return for a scheduled visit, every effort should be made to contact the subject. In any circumstance, every effort should be made to document subject outcome, if possible. The Investigator should inquire about the reason for withdrawal and request that the subject return for the EOS follow-up visit (complete procedures at final safety visit) and follow up with the subject regarding any unresolved adverse events.

If the subject withdraws from the study and also withdraws consent for disclosure of future information, no further evaluations should be performed, and no additional data should be collected. The Sponsor may retain and continue to use any data collected before such withdrawal of consent.

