12. BIOMARKER AND IMMUNOGENICITY ANALYSIS

Biomarker data, e.g. P-selectin, will be summarized for each time point using descriptive statistics (number of subjects, mean, SD, median, minimum, and maximum). A listing will be presented by subject.

The PB2452 antibodies will be summarized by visit and treatment. A listing for subjects will also be provided by treatment and visit.

If positive ADA is observed, results may be reported by ADA status for AEs, efficacy and pharmacokinetics. An ADA-positive subject is defined as a subject with at least one ADA-positive sample at any time during the treatment or follow-up observation period. In case of a positive pre-treatment sample, if the titer of at least one post-treatment ADA is elevated at least 2 folds of the titer in pre-treatment sample, this subject is also ADA positive. In all other cases, a subject is considered negative for ADA.

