13. ANALYSIS CONVENTIONS

Post-text tables and listings will be prepared in accordance with the current ICH Guidelines. The information and explanatory notes to be provided in the “footer” or bottom of each table and listing will include the following information:

1. Date and time of output generation;
2. SAS® program name that generates the output;
3. Any other output specific details that require further elaboration.

In general, tables will be formatted with a column displaying findings for all subjects combined. Row entries in tables are made only if data exists for at least one subject (i.e., a row with all zeros will not appear). The only exception to this rule applies to tables that list the termination status of subjects (e.g., reasons for not completing the study). In this case, zeros will appear for study termination reasons that no subject satisfied. The summary tables clearly indicate the number of subjects to which the data apply and unknown or not performed are distinguished from missing data.

This section details general conventions to be used for the statistical analyses. The following conventions will be applied to all data presentations and analyses.

- All summary tables will include the analysis set sample size (i.e., number of subjects).
- Study Day 1 is defined as the first day the subject is exposed to the study drug. All *study days* are determined relative to the day of exposure to the study drug
- Baseline values will be defined as those values recorded closest to, but prior to, the first study treatment on Day 1 for all measurements except for PD/efficacy endpoints. For these endpoints baseline is the last value before ticagrelor is administered.
- Change from baseline will be calculated as follows:

$$\text{Change} = \text{Post-baseline value} - \text{baseline value}.$$

- Subject data obtained during unscheduled visits/assessments will not be summarized but will be included in subject data listings only; except for the determination of minimum % inhibition of PRU or PRI within 4 hours post-baseline. Unscheduled visit values will not be used to impute missing scheduled visit values, except for baseline calculation.
- No visit windows will be used to select efficacy data for analysis. Data collected at the nominal visit will be used for analysis (note that Day 35 is defined as 35 \pm 3, but will be reported as Day 35/End-of-study for simplification).

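### SAP 12 classes dosed subjects with no post-dose ADA result as ADA-negative, because negative status requires no post-dose sample

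*SAP*

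**What the plan says.** SAP 12 defines ADA status per subject in three steps.

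- The general rule: "An ADA-positive subject is defined as a subject with at least one ADA-positive sample at any time during the treatment or follow-up observation period".
- For a subject already positive before treatment, a subject also counts as positive "if the titer of at least one post-treatment ADA is elevated at least 2 folds of the titer in pre-treatment sample".
- The remainder: "In all other cases, a subject is considered negative for ADA".

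The same section provides for using this status: "If positive ADA is observed, results may be reported by ADA status for AEs, efficacy and pharmacokinetics". It also plans an antibody summary by visit and treatment, with a listing.

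On sampling, Protocol section 6 states that antibodies "will be assessed in all subjects at Day -3, Day 1 (randomization), Day 7" and Day 35±3. A note to the Protocol's schedule of events requires the Day 1 sample to be drawn before the infusion starts. Discharge is on Day 3. SAP 10 reports antibodies to study drug in the Safety Population, which SAP 5 defines by receipt of any amount of study drug.

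**The concern.** A negative ADA status should mean that the subject was tested after exposure and no response was found. Under SAP 12 it means only that no positive finding is on record. A dosed subject with no post-dose sample cannot meet the titer rule. Unless a pre-dose positive is counted under the general rule, that subject falls into the closing category and is recorded as negative.

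Immunogenicity is part of a named secondary objective, and the Protocol's risk section lists hypersensitivity-type reactions and antibody formation among the potential risks. Two results could be affected. A subject-level ADA incidence would be understated, since untested subjects would be in the denominator and could not be in the numerator. A comparison of adverse events, efficacy or PK by ADA status would have untested subjects in its negative group. If someone left after a reaction and was never sampled, the event would appear among the ADA-negatives with no evidence that it belongs there.

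**Working it through.** **1. Can the case arise?** Of the four routine ADA samples, Day -3 and Day 1 are pre-dose, and Day 7 and Day 35±3 are post-dose. Both post-dose samples fall after the Day 3 discharge. A dosed subject lost after discharge has none. The same holds for one who withdraws and also withdraws consent to further disclosure, since Protocol 6.2.1.2 then ends all evaluation. A subject missing only one of the two still has a post-dose result and is not in question here.

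**2. Does another provision catch it?**

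- SAP 5 defines no ADA-evaluable population.
- SAP 6.3 drops missing data from proportions for binary endpoints, but the sentence follows directly on the one about efficacy endpoints and does not name ADA. Even if it applied, the closing rule of SAP 12 leaves no status missing to be dropped.
- SAP 13 asks tables to separate tests not performed from missing data. That governs display and does not change the status definition.
- Protocol 9.3.8 adds no evaluability rule.
- Replacing a withdrawn subject does not take the dosed subject out of the Safety Population.

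**3. Pre-existing antibodies.** Protocol 2.1.4 reports that 15 of 48 PB2452 subjects in Phase 1 (31%) were positive before dosing. For such a subject with no post-dose titer, SAP 12 gives negative, or gives positive if the Day 1 pre-dose sample is read as part of the treatment period. Neither is known to be right.

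**4. Size.** The plan states no ADA figure for this trial, so there is none to reproduce. The inputs are:

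- r, the rate among tested subjects: 6/48 = 12.5% became positive after PB2452 in Phase 1 (Protocol 2.1.4).
- N = 150 on PB2452 (SAP 4.2).
- m, the share with no post-dose result: not in the documents, assumed at 2%, 5% and 10%.

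Untested = N × m. Positives = r × N × (1 − m). Rate under SAP 12 = positives / N = r × (1 − m). Rate among evaluable subjects = r. Untested share of the negative group = N × m / (N − positives).

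| m | Untested | Positives | Rate under SAP 12 | Rate among evaluable | Untested share of negatives |
|---|---|---|---|---|---|
| 2% | 3.0 | 18.4 | 12.25% | 12.5% | 3.0/131.6 = 2.3% |
| 5% | 7.5 | 17.8 | 11.9% | 12.5% | 7.5/132.2 = 5.7% |
| 10% | 15.0 | 16.9 | 11.25% | 12.5% | 15.0/133.1 = 11.3% |

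The incidence falls by 0.25, 0.6 and 1.25 percentage points.

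**5. Primary analysis.** It does not use ADA status. The stated power of more than 99% (difference 15, SD 20, 150 against 50, two-sided 0.05) reproduces as 99.6% and is unaffected.

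**The case against.** The strongest reply is that little in the plan depends on the sentence. The planned antibody summary is by visit and rests on samples, so someone with no Day 7 sample need not appear as a Day 7 negative. No subject-level incidence table is specified, and reporting by ADA status is optional and conditional on a positive finding. The number affected should also be low: this is a single infusion with confinement to Day 3, subjects may stay on site for the later visits, and Protocol 6.2.1.1 asks that subjects who received all or part of the infusion complete the remaining visits. All of this stands. It limits the size of the problem but does not correct the definition, which would apply wherever subject-level status is used.

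Two stronger readings are tempting, and the documents support neither.

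- A reader might infer that a subject whose infusion is stopped has no post-dose sample. Stopping the infusion is not leaving the study, and the Protocol asks for continued follow-up.
- A reader might infer that an end-of-study sample drawn a few days after dosing would be analysed as a Day 35 negative. For a subject who refuses to return, Protocol 6.2.1.1 says the Day 35 "visit procedures should be completed to the extent possible", and 6.2.1.2 has the investigator "request that the subject return for the EOS follow-up visit". Neither sets an early date. The SAP 13 convention "Data collected at the nominal visit will be used for analysis" stands in a bullet that opens with efficacy data and that itself defines Day 35 as 35±3. No error follows for ADA, laboratory, ECG or PK summaries.

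**Conclusion.** The point holds for subject-level ADA status. A dosed subject with neither a Day 7 nor a Day 35 result is classed as negative by an explicit rule, and no other provision corrects it. This is a wrong classification written into the SAP, not merely a missing detail. It carries into displays by ADA status only if those are produced. It should not be read as a defect in the by-visit antibody summary.

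Any subject-level incidence is multiplied by (1 − m), always downward. The figures rest on the Phase 1 rate of 12.5% and on assumed values of m; 10% is probably high for this design. They also treat the rate among tested subjects as the rate of interest, which requires that being untested is unrelated to antibody response. The effect on incidence is probably small. The effect on a comparison of rare events by ADA status cannot be sized from the documents.

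**What to change.** Replace the last sentence of SAP 12 with:

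> ADA-negative requires at least one evaluable post-dose ADA result and no result meeting the positive definition. Dosed subjects with no evaluable post-dose ADA result are not evaluable and are excluded from the ADA incidence denominator and from comparisons by ADA status. Their number is reported by arm.

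The change needs no new data and can be made before the SAP is signed, which the SAP places ahead of database lock. The cost is a slightly smaller denominator. The count by arm lets a reader see whether untested subjects are few and evenly spread. SAP 13 needs no change on this account.

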13. ANALYSIS CONVENTIONS

Post-text tables and listings will be prepared in accordance with the current ICH Guidelines. The information and explanatory notes to be provided in the “footer” or bottom of each table and listing will include the following information:

1. Date and time of output generation;
2. SAS® program name that generates the output;
3. Any other output specific details that require further elaboration.

In general, tables will be formatted with a column displaying findings for all subjects combined. Row entries in tables are made only if data exists for at least one subject (i.e., a row with all zeros will not appear). The only exception to this rule applies to tables that list the termination status of subjects (e.g., reasons for not completing the study). In this case, zeros will appear for study termination reasons that no subject satisfied. The summary tables clearly indicate the number of subjects to which the data apply and unknown or not performed are distinguished from missing data.

This section details general conventions to be used for the statistical analyses. The following conventions will be applied to all data presentations and analyses.

- All summary tables will include the analysis set sample size (i.e., number of subjects).
- Study Day 1 is defined as the first day the subject is exposed to the study drug. All *study days* are determined relative to the day of exposure to the study drug
- Baseline values will be defined as those values recorded closest to, but prior to, the first study treatment on Day 1 for all measurements except for PD/efficacy endpoints. For these endpoints baseline is the last value before ticagrelor is administered.
- Change from baseline will be calculated as follows:

$$\text{Change} = \text{Post-baseline value} - \text{baseline value}.$$

- Subject data obtained during unscheduled visits/assessments will not be summarized but will be included in subject data listings only; except for the determination of minimum % inhibition of PRU or PRI within 4 hours post-baseline. Unscheduled visit values will not be used to impute missing scheduled visit values, except for baseline calculation.
- No visit windows will be used to select efficacy data for analysis. Data collected at the nominal visit will be used for analysis (note that Day 35 is defined as 35 \pm 3, but will be reported as Day 35/End-of-study for simplification).
- Date-time variables will be formatted as *yyyy-mm-ddThh:mm* for presentation (i.e., in ISO8601 format).
- Date variables will be formatted as *yyyy-mm-dd* for presentation.

- SAS® Version 9.4¹ or higher will be the statistical software package used for all data analyses.
- The study visit and subject number will be included in all data listings. All listings will be sorted by subject number and visit date, as applicable.

